#### **4.2 Additional echocardiogram and data available**

In the event that more than 1 echocardiogram or required data point is performed and available within a specific study data collection timepoint, the data closest to the study timepoints will be used for the primary analysis. However, all available data should be collected in additional applicable CRFs. Additional echocardiograms should be submitted to the echocardiogram core lab for analysis.

#### **4.3 Measures Taken to Avoid Bias**

In order to avoid bias, a Clinical Events Committee (CEC) will be used to review and adjudicate events of interest noted in the Safety Reporting and Committees section. The CEC adjudication (including relationship to procedure and device) will be used for the primary analysis. An Echocardiogram Core Lab will be used to assess echocardiographic data points. Echocardiogram assessments will be used for the primary analysis. Physicians and staff involved with the study CEC and core lab will not be participating as Primary Investigators in this study. All patients that underwent a Portico ViV procedure will be screened for eligibility and enrollment as study subjects, regardless of procedure success. All eligible subjects, regardless of their outcome or survival should be considered for screening and enrollment.

### **5 ENDPOINTS**

#### **5.1 Primary Safety Endpoint**

Composite of all-cause mortality, disabling stroke, life threatening bleeding requiring blood transfusion, acute kidney injury (AKI) requiring dialysis, and major vascular complications at 30 days.

#### **5.2 Primary Performance Endpoint**

Composite of all-cause mortality or disabling stroke at 1 year.

#### **5.3 Descriptive Endpoints**

##### **Descriptive Endpoints:**

###### **1. Procedure success defined as:**

- Absence of procedural mortality AND
- Successful access, delivery of the valve, and retrieval of the delivery system

###### **2. Evaluation of adverse event rates**

###### At 30 days and one year:

- All-cause mortality
- Cardiovascular-related mortality
- All Stroke (by severity)
- Transient Ischemic Attacks (TIA)
- Myocardial infarction (MI)
- New pacemaker implant (PPI)
- Coronary obstruction

At 30 days:

- Minor, Major, and Life-threatening bleeding
- Major vascular, major non-vascular access-related, or cardiac structure complication
- Acute Kidney Injury (AKI) stages 1-4

3. Evaluation of adverse event rates annually through 5 years:

- All-cause mortality
- Cardiovascular-related mortality
- All Stroke (by severity)
- TIA

The following will be collected if standard of care or if available:

4. Echocardiographic assessment of valve performance at discharge, 30 days, 1 year, and annually through 5 years including:

- Transvalvular mean gradient
- Indexed Effective orifice area (iEOA)
- Doppler velocity index (DVI)
- Aortic Valve Area (AVA)
- Non-structural valve dysfunction:
  - Prosthetic patient mismatch (PPM) per body mass index (BMI)
  - Degree of aortic valve regurgitation (transvalvular and paravalvular leak (PVL)) as none/trace, mild, mild-moderate, moderate, moderate/severe, or severe per VARC-3; and per VARC-2 none/trace, mild, moderate, or severe).

5. Valve Integrity at 1 year and annually through 5 years as assessed by:

- Structural Valve Deterioration (SVD) (by hemodynamic valve deterioration (HVD) stages 1-3 per VARC-3)

Confirmed intrinsic permanent changes to the prosthetic valve, including:

- Wear and tear
- Leaflet disruption
- Flail leaflet
- Leaflet fibrosis and/or calcification
- Strut fracture or deformation

- Non-structural Valve Dysfunction other than PVL and PPM (HVD stages 1-3 per VARC-3)

Any abnormality not intrinsic to the prosthetic valve resulting in valve dysfunction other than PVL and PPM, including:

- Leaflet entrapment by pannus or tissue
- Inappropriate positioning or sizing
- embolization

- Clinically Significant Thrombosis

Meeting either of the following criteria:

- Clinical sequelae of thromboembolic event or worsening AS/transvalvular AR and HVD Stage 2-3 or confirmatory imaging of thrombosis

Or

- In the absence of clinical sequelae, both HVD Stage 3 and confirmatory imaging

- Endocarditis (by HVD stages 1-3 per VARC-3)

Meeting at least one of the following criteria:

- Fulfilment of the Duke endocarditis criteria
- Evidence of abscess, pus, or vegetation confirmed as secondary to infection by histological or microbiological studies during re-operation
- Evidence of abscess, pus or vegetation confirmed on autopsy.

The following definitions of HVD Stages (1-3) will be used when assessing valve integrity.

- Stage 1 (Morphological Valve Deterioration):

Evidence of SVD, non-structural valve dysfunction (other than paravalvular or PPM), thrombosis or endocarditis without significant hemodynamic changes.

- Stage 2 (Moderate hemodynamic valve deterioration):

Increase in mean transvalvular gradient  $\geq 10$  mmHg resulting in mean gradient  $\geq 20$  mmHg with concomitant decrease in EOA  $\geq 0.3 \text{ cm}^2$  or  $\geq 25\%$  and/or decrease in Doppler velocity index  $\geq 0.1$  or  $\geq 20\%$  compared with echocardiographic assessment performed 1-3 months post-procedure, OR new occurrence or increase of  $\geq 1$  graded of intra-prosthetic AR resulting in  $\geq$  moderate AR

- Stage 3 (Severe hemodynamic valve deterioration):

Increase in mean transvalvular gradient  $\geq 20$  mmHg resulting in mean gradient  $\geq 30$  mmHg with concomitant decrease in EOA  $\geq 0.6 \text{ cm}^2$  or  $\geq 50\%$  and/or decrease in Doppler velocity index  $\geq 0.2$  or  $\geq 40\%$  compared with echocardiographic assessment performed 1-3 months post-procedure, OR new occurrence, or increase of  $\geq 2$  grades, of intra-prosthetic AR resulting in severe AR.

- Any need for Portico TAVI re-intervention after implant through 5 years

6. Clinical benefit endpoints defined as improvement from baseline to 30 days, 1 year, and annually through 5 years from index procedure, including:

- New York Heart Association (NYHA) functional classification

## 6 SUBJECT SELECTION AND WITHDRAWAL

### 6.1 Study Population

This study will enroll subjects of all genders from the general population of patients that have had a failed surgical bioprosthetic aortic valve procedure with a subsequent Portico™ ViV attempted implant. Patients must meet all general eligibility criteria and provide written informed consent prior to being included in this retrospective data-collection study.

For the exploratory registry arm, patients that had an inner aortic diameter  $< 19$  mm or  $> 27$  mm of the surgical aortic bioprosthetic valve will be included in this registry arm. Data collected in this registry arm will not be included in the primary analyses.

## 6.2 Subject Recruitment and Screening

A member of the site's study team trained to the protocol must evaluate patients for the general study eligibility criteria, and if applicable, will enter the patients into a site-specific recruitment/screening log. A patient who does not satisfy all general eligibility criteria prior to informed consent is considered a recruitment failure and should not be enrolled in the study.

Sites will ask patients meeting general inclusion criteria and no general exclusion criteria to sign an Informed Consent Form (ICF) following the established Informed Consent process if they wish to participate in this data-collection study. Sites will enter these patients into the recruitment/screening log. Once a duly dated and signed ICF is obtained, sites will begin the protocol data collection assessments as part of the study screening process.

Subjects who do not meet the study eligibility criteria are considered a screen failure and should not be enrolled in the study. The Principal Investigator or the delegated study personnel will record the screen failure in the hospital records and on a recruitment/screening log as required.

## 6.3 Informed Consent

Patients that have had a failed surgical aortic bioprosthetic valve and underwent a Portico ViV Implant procedure may be identified and screened as potential study subjects. Patients may be identified from their study site's procedure records for potential study enrollment. Once identified, each patient must complete the informed consent process prior to study participation.

The Principal Investigator or his/her authorized designee will conduct the Informed Consent process, as required by applicable regulations and the center's local Ethics Committee (EC). This process will include a verbal discussion with the patient on all aspects of the study which are relevant to the patient's decision to participate, such as details of data being collected, any potential benefits and potential risks of participation. During the discussion, the Principal Investigator or his/her authorized designee will avoid any improper influence on the patient and will respect the patient's legal rights. The patient must be provided with the Informed Consent Form (ICF) written in a language that is understandable to the subject and has been approved by the center's local EC. The patient must have adequate time to review, ask questions and consider participation.

If the patient agrees to participate and signs the ICF, the ICF must be signed and dated by the subject and by the person who obtained the subject's consent. The signed original form will be filed in the subject's hospital or research charts, and a copy will be provided to the subject by the Investigator or his/her authorized designee.

The Principal Investigator or his/her authorized designee will document the informed consent process in the subject's hospital/clinic and/or research charts. The date of signature will be entered on an applicable Case Report Form (CRF).

Failure to obtain the ICF from a subject prior to study enrollment should be reported to the Sponsor within 5 working days and to the study site's EC according to their reporting requirements.

If, during the study, new information becomes available that can significantly affect a subject's future health and medical care, the Principal Investigator or his/her authorized designee will

provide this information to the subject. If relevant, the subject will be asked to confirm their continuing informed consent in writing.

#### **6.4 Informed Consent and Enrollment of the Deceased**

For patients that are deceased at enrollment time but underwent a previous Portico ViV procedure to replace a failed surgical bioprosthetic valve, all institutional/local legal and regulatory requirements must be met prior to enrollment and data collection.

### **7 ELIGIBILITY CRITERIA**

#### **7.1 Inclusion Criteria**

1. Subject had a degenerated surgical aortic bioprosthetic valve with severe aortic stenosis, severe regurgitation, or a combination of at least moderate stenosis with at least moderate regurgitation per EAPCI-ESC-EACTS standardized criteria.
2. Surgical bioprosthetic true inner diameter (true ID) was  $\geq 19$  mm and  $\leq 27$  mm and was confirmed by either CT or confirmed by the Valve in Valve Aortic App. Refer to the PCR website <https://www.pcronline.com/PCR-Publications/PCR-mobile-apps/Valve-in-Valve-Aortic-app> Note: if CT was contraindicated and/or not possible to be obtained, a transesophageal echocardiogram (TEE) will be accepted for sizing.
3. Prior to Portico ViV procedure, the patient was deemed at increased risk for surgery to replace the surgical aortic bioprosthetic valve.
4. Subject provided written informed consent prior to performing data collection for study specific visits. For patients that are deceased at the time of enrollment, all institutional/local legal and regulatory requirements for consent must be met prior to enrollment and data collection.
5. Subject is  $\geq 18$  years of age or legal age in host country at the time of consent.
6. Prior to the Portico ViV index procedure, the subject had New York Heart Association (NYHA) class II, III, or IV.
7. Subject had a minimum vessel diameter of 6.0 mm for Portico™ delivery system access or a minimum of 5.0 mm for the FlexNav™ delivery system.
8. Subject had the Portico or FlexNav delivery system enter their vasculature with the intent of replacing a failed aortic bioprosthetic valve.

## 7.2 Exclusion Criteria

Exclusion criteria is from the time of the Portico ViV index procedure:

1. Subject had evidence of an acute MI, percutaneous intervention, or a peripheral intervention  $\leq$ 30 days prior to Portico ViV index procedure (MI defined as: ST Segment Elevation as evidenced on 12 Lead ECG).
2. Subject had uncontrolled blood dyscrasias defined as: leukopenia (WBC $<$ 3,000 mm $^3$ ), acute anemia (Hb  $<$ 9 g/dL), or thrombocytopenia (platelet count  $<$ 50,000 cells/mm $^3$ ).
3. Subject was considered hemodynamically unstable at the time of the ViV procedure (requiring inotropic support or mechanical heart assistance)
4. Subject had severe ventricular dysfunction with left ventricular ejection fraction (LVEF)  $<$ 20% as measured by resting echocardiogram.
5. Subject had imaging evidence of intracardiac mass, thrombus or vegetation.
6. Subject had an active peptic ulcer or has/had upper gastrointestinal (GI) bleeding  $\leq$ 3 months prior to ViV index procedure.
7. Subject had a documented history of a cerebrovascular accident (CVA) or a transient ischemic attack (TIA)  $\leq$ 6 months prior to index procedure.
8. Subject had renal insufficiency (serum creatinine  $>$ 3.0 mg/dL (265.5 $\mu$ mol/L)) and/or end stage renal disease requiring chronic dialysis.
9. Subject had active bacterial endocarditis or ongoing sepsis  $\leq$  6 months prior to the index procedure.
10. Surgical aortic bioprosthetic valve was unstable or rocking.
11. Subject had a vascular condition (i.e. stenosis, tortuosity, or severe calcification) that made insertion and endovascular access to the aortic valve impossible.
12. Subject was unable to tolerate antiplatelet or anticoagulant therapy.

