## 2.0 ANALYSIS CONSIDERATIONS

#### 2.1 Analysis Population

#### 2.1.1 **Primary Analysis Population**

The primary analysis population will include patients who have signed an Informed Consent Form (ICF), or for those patients deceased at the time of study screening, all local and national regulatory requirements were met for consent, and at minimum, the Portico delivery system entered his/her vasculature for an attempted Portico ViV implant. Subjects that are enrolled and later determined to be screen failures (those that do not meet all inclusion criteria or meet any exclusion criteria) will not be included in any analysis. Subjects that are enrolled in the Exploratory Arm of the study will not be included in the primary arm of the study.

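### Exclusion 3 does not separate instability present before the procedure from collapse during it, so a complication can become a reason for exclusion

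*Protocol*

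**What the plan says.** Item 3 of Protocol 7.2 excludes a patient where "Subject was considered hemodynamically unstable at the time of the ViV procedure (requiring inotropic support or mechanical heart assistance". The list stands under one lead-in, "Exclusion criteria is from the time of the Portico ViV index procedure", and the synopsis uses the same phrase.

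The items are dated differently. Items 1, 6, 7 and 9 look back over a stated period before the index procedure. Item 3 refers to the time of the procedure itself. Items 2 (blood counts), 8 (renal function) and 12 ("Subject was unable to tolerate antiplatelet or anticoagulant therapy") carry no date. Item 11 is defined by a result: "Subject had a vascular condition (i.e. stenosis, tortuosity, or severe calcification) that made insertion and endovascular access to the aortic valve impossible".

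Inclusion 8 (Protocol 7.1) requires that the delivery system already entered the vasculature, so every candidate has had the procedure when eligibility is judged. Protocol 4.3 states: "All patients that underwent a Portico ViV procedure will be screened for eligibility and enrollment as study subjects, regardless of procedure success". Protocol 9.4 (item 5) and 11.6.1 keep subjects whose valve was not implanted and follow them to 30 days. Protocol 5.3 makes successful access part of procedure success.

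A patient found ineligible after enrolment is excluded with a deviation form (Protocol 8.1). SAP 2.1.1 says of such subjects: "those that do not meet all inclusion criteria or meet any exclusion criteria) will not be included in any analysis".

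**The concern.** In a prospective study, an exclusion for haemodynamic instability is applied before the outcome exists. Here it is applied from a chart that records what happened on the table. If support given because of a complication counts as the excluded state, membership of the analysis set depends on the outcome.

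The subjects at risk of removal are those who collapsed during the implant, a group in which deaths and serious events are to be expected. Such events feed the 30-day composite, and the deaths among them also feed the 1-year composite. Two sites could read the same chart differently and both be within the text.

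**Working it through.** **1. Does item 3 reach support started during the implant?** The lead-in can mean *as of* the procedure or *from then on*. Item 3 has its own time phrase, which is the procedure itself, and the state is defined by the support required. Support first started during deployment is support at the time of the procedure, so item 3 reaches it under either reading of the lead-in. The look-back items show that the protocol states a pre-procedure period when it intends one.

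**2. Can the subject come back into the analysis?** No route was found.
- Protocol 4.3 governs screening and still applies eligibility.
- Protocol 8.1 and SAP 2.1.1 remove the subject even after enrolment.
- Protocol 11.6 says that adverse events are not collected for screen failures, so the events of a patient excluded at screening are not in the database.
- The sensitivity analyses in SAP 2.12 vary COVID-19 relatedness and the VARC version only.
- The Clinical Events Committee can adjudicate only the subjects who remain.

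**3. Which way does the rate move?** Let x of n subjects have the 30-day event, and let r subjects be removed, e of them with the event. The observed rate is (x − e)/(n − r). It is below x/n exactly when e/r > x/n, that is, when the removed subjects have a higher event rate than the whole group. This is likely for patients who collapsed during the implant, but the documents do not show it. Needing inotropes is not itself a component of the composite.

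**4. Size, as an illustration only.** The plan gives no expected rate, so there is no figure to reproduce. From the documents: n = 100, the stated maximum for the primary population (SAP 1.3), and the exact Clopper-Pearson interval (SAP 2.3.1.1). Assumed: x = 12, r and e. With a observed events among m remaining subjects, the limits are the 0.025 quantile of Beta(a, m − a + 1) and the 0.975 quantile of Beta(a + 1, m − a).

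| Removed (r) | With event (e) | Observed | Rate | Exact 95% CI |
|---|---|---|---|---|
| 0 | 0 | 12/100 | 12.0% | 6.4 to 20.0 |
| 1 | 1 | 11/99 | 11.1% | 5.7 to 19.0 |
| 3 | 3 | 9/97 | 9.3% | 4.3 to 16.9 |
| 3 | 0 | 12/97 | 12.4% | 6.6 to 20.6 |
| 5 | 5 | 7/95 | 7.4% | 3.0 to 14.6 |
| 5 | 2 | 10/95 | 10.5% | 5.2 to 18.5 |

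For other assumed true counts with r = e = 3: 10/100 becomes 7/97 = 7.2% (3.0 to 14.3), and 20/100 becomes 17/97 = 17.5% (10.6 to 26.6).

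**5. The other items.**
- *Items 2, 8 and 12.* These depend wholly on the lead-in. Read as *as of* the procedure, a low haemoglobin, a raised creatinine or drug intolerance that appears after a complication does not count. Read as *from then on*, or with no date applied, it does. Items 4, 5 and 10 are also undated.
- *Item 11.* A patient whose system never entered already fails inclusion 8. Read literally, with insertion and access both impossible, item 11 removes nobody who meets inclusion 8. Read loosely, it removes patients whose system entered but could not reach the valve. Those are the cases that Protocol 4.3, 5.3, 9.4 and 11.6.1 keep and count.

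**The case against.** The strongest reply is that the lead-in sets one reference date for the whole list. In a retrospective study its natural purpose is to judge status as of the index procedure and not as of consent years later. *From then on* fits badly with the look-back items under the same lead-in. Protocol 4.3 also says that eligible subjects should be considered whatever their outcome or survival. Screen failures are logged (Protocol 6.2) and late exclusions leave a deviation form, so removals can be traced. No hypothesis is tested (SAP 2.10), so no pass or fail decision turns on the rate.

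Much of this stands, and it limits the point. A reader might infer that items 3, 11 and 12 together strip out collapses, access failures and bleeds, and that the rates are shown to be biased in favour of the device. The documents do not support that. Item 12 reaches intolerance after a bleed only on the less natural reading of the lead-in. Item 11 removes nobody on its literal wording, so it is an inconsistency to resolve and not a demonstrated bias. The direction of any shift depends on the event rate among those removed, which is unknown, and removing subjects without events would raise the observed rate.

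The reply does not dispose of item 3. Dating the list to the procedure does not help when the item is met by what happens during the procedure. A log makes removals traceable but does not return them to the analysis.

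**Conclusion.** The point holds for item 3. As written it can exclude a subject for support first needed because of a complication during the implant, and the plan then omits that subject everywhere. The likely effect is a lower 30-day safety rate and a lower 1-year rate of death or disabling stroke.

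The number affected and the exact shift cannot be derived from the documents. On the assumed 12/100, losing 3 subjects who all had events moves the rate by 12.0 − 9.3 = 2.7 percentage points. That is less than the half-width of the full-sample interval, (20.0 − 6.4)/2 = 6.8 points, but it is a selection bias that the planned interval does not reflect. The shift is smaller if some of those removed had no event.

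Items 2, 8 and 12 carry a lesser risk that depends on an ambiguous lead-in. Item 11 needs reconciling. Because the affected number is unknown and no test depends on it, this should be fixed before analysis but is not a fatal flaw.

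**What to change.** Replace the lead-in of Protocol 7.2, and the matching line in the synopsis, with one sentence to this effect: *Every exclusion, including item 3, is judged on the subject's status as documented before the delivery system entered the vasculature; a condition that first arises after that point, during or after the index procedure, is an outcome and not a reason for exclusion.*

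Leave the clinical thresholds and the look-back periods in items 1, 6, 7 and 9 as they are. One sentence for the whole list is better than rewording single items, which would suggest that the others may be met afterwards.

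Reconcile item 11 with inclusion 8 and with Protocol 4.3, 5.3, 9.4 and 11.6.1, so that it is clear whether it removes anyone whose delivery system entered.

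Re-check subjects logged as screen failures, or excluded after enrolment, under item 3, item 11 and the undated items against the new sentence. Report the number excluded under each item.

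The cost is one sentence, the reconciliation of item 11 and a log check. The reported rates may become slightly less favourable.

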## 7.3 Exploratory Registry Arm Inclusion and Exclusion Criteria

For inclusion in the Exploratory Registry Arm, the eligibility required is the same as listed above, with the exception of the following:

